5.3 Use of radiation: NA

5.4 Use of Center for Magnetic Resonance Research: NA

6.0 Data and Specimen Banking

6.1 Storage and Access: The individual participant study data will be collected in the smartphone application during the research encounter, under an assigned ID#. Once the data has been collected and uploaded to a secure web-based data storage site (Box) the individual devices will be cleared of any individual participant data.

MEDICAL PROTOCOL (HRP-590)

PROTOCOL TITLE: Capillary Refill Time Measurement Utilizing Mobile Application (Cap App) in Children

VERSION DATE: 10/27/2022

1.4 Data: Study data will be uploaded from the smartphone application to a secure web-based platform (Box) for access by study team members only. The data (de-identified) will be shared with the University of Washington under a Data Use Agreement (DUA). The DUA is in process with SPA. De-identified data will be stored in Box for future use by other researchers. Data will be available immediately following study completion with no end date. Researchers, including those outside the study, whose proposed use of the data has been approved by the PI will have access to the data to achieve aims in the approved proposal. AHC-IE will not be used.

For publishing of data derived from the study: Publishing of these data may be required. Federal funders, granting agencies, and journal publishers increasingly require datasets be made publicly available-often immediately upon associated article publication. If this is the case, all data published will be fully de-identified.

6.2 Release/Sharing: Should the investigators pursue data sharing, future studies seeking to compile data acquired from this protocol will obtain IRB approval before doing so. In the event that this occurs, only investigators or study personnel listed in an IRB-approved protocol pertaining to the data compilation will have access to this data. The requested data will be released to the researchers in a de-identified manner. Any scientist who is willing to partner with a study investigator may submit a manuscript proposal or an ancillary study proposal. Once the PI approves the proposal, the investigator and the data coordinating center enter into a Data Use Agreement (DUA). After the signing of the agreement, this institution and coordinating team will distribute the requested data to the investigator. A nominal fee is charged for preparing the datasets.

7.0 Sharing of Results with Participants

7.1 There are no plans on sharing results of the individual participant study data or aggregate study data with the participants. The data will be kept blinded from the research team members at the time of collection and, thus, no information will be shared with the participants.

7.2 Sharing of genetic testing: NA

8.0 Study Population

8.1 Inclusion Criteria: Healthy children aged 1 month – 17 years.

8.2 Exclusion Criteria:

- Fever or hypothermia
- Chronic illness including cardiovascular or renal disease
- Severe injury or blood loss

MEDICAL PROTOCOL (HRP-590)

PROTOCOL TITLE: Capillary Refill Time Measurement Utilizing Mobile Application (Cap App) in Children

VERSION DATE: 10/27/2022

- Dehydration (including vomiting and/or diarrhea)
- Raynaud's phenomenon
- Children who do not have a parent or legal guardian present to obtain consent

8.3 Screening: Convenience sample of participants presenting at the D2D: The Driven to Discover Research Facility at the Minnesota State Fair August 25 - September 5, 2022 will be screened for inclusion and exclusion criteria. All those who are eligible will have the opportunity to enroll. We will utilize a script to assist in the screening process to ensure that all information is presented accurately and uniformly to all potential participants.

9.0 Vulnerable Populations

9.1 Vulnerable Populations:

| Population / Group | Identify whether any of the following populations will be focus of the research (targeted), included, but not necessarily the focus or excluded from participation in the study. |
|----------------------------------------------------------------------------------------------------------------------------------------------------------------------------------------------------------------------------------------------------------|----------------------------------------------------------------------------------------------------------------------------------------------------------------------------------|
| Children | Primary focus of the research |
| Pregnant women/fetuses/neonates | Excluded |
| Prisoners | Excluded |
| Adults lacking capacity to consent and/or adults with diminished capacity to consent, including, but not limited to, those with acute medical conditions, psychiatric disorders, neurologic disorders, developmental disorders, and behavioral disorders | Excluded |
| Non-English speakers | Excluded |
| Those unable to read (illiterate) | included but not the focus |
| Employees of the researcher | Excluded |

MEDICAL PROTOCOL (HRP-590)

PROTOCOL TITLE: Capillary Refill Time Measurement Utilizing Mobile Application (Cap App) in Children
VERSION DATE: 10/27/2022

| | |
|-------------------------------------------------------------------------------------------------------------------------------------------------------------------------------|----------------------------|
| Students of the researcher | Excluded |
| Undervalued or disenfranchised social group | included but not the focus |
| Active members of the military (service members), DoD personnel (including civilian employees) | Excluded |
| Individual or group that is approached for participation in research during a stressful situation such as emergency room setting, childbirth (labor), etc. | Excluded |
| Individual or group that is disadvantaged in the distribution of social goods and services such as income, housing, or healthcare. | included but not the focus |
| Individual or group with a serious health condition for which there are no satisfactory standard treatments. | included but not the focus |
| Individual or group with a fear of negative consequences for not participating in the research (e.g. institutionalization, deportation, disclosure of stigmatizing behavior). | included but not the focus |
| Any other circumstance/dynamic that could increase vulnerability to coercion or exploitation that might influence consent to research or decision to continue in research. | included but not the focus |

9.2 Additional Safeguards, if any, to ensure inclusion is appropriate:

Children: This research is designed specifically to assess the effectiveness of a mobile health application to measure CRT in children; therefore, children must be included in the study to answer the research question. Children are the targeted population for this study because the study aims could not be assessed without children. Study procedures have been minimized to exclude all unnecessary

MEDICAL PROTOCOL (HRP-590)

PROTOCOL TITLE: Capillary Refill Time Measurement Utilizing Mobile Application (Cap App) in Children
VERSION DATE: 10/27/2022

procedures that would not contribute to the scientific objective. All participants will be provided assurance of confidentiality, the freedom to decline to participate and the right to withdraw at any time without penalty. Consent process for children is described in section 21.5

Individual or group that is approached for participation in research during a stressful situation such as emergency room setting, childbirth (labor), etc.: All efforts will be made to consent the patient or LAR during a non-stressful time. Extra caution will be taken as to not coerce the potential participant. They will be encouraged to ask questions of the research team or and discuss with their support if needed. Individuals who are noticeably nervous or stressed at that time will not be consented.

Those unable to read (Illiterate): Patients and/or their LAR who are illiterate may not be known, research staff will not be asking a direct question about literacy to potential participants. However, if it is made known to us that the patient or their LAR is illiterate, we will take extra care to go through the consent form and read it to the potential participant. An unbiased witness (non- study team member) will be present to attest that the consent form was described accurately. This witness will also sign the consent form.

Individual or group that is disadvantaged in the distribution of social goods and services such as income, housing, or healthcare: Undervalued or disadvantaged people may not be known, research staff will not be asking a direct question about socioeconomic status to potential participants. The voluntary nature of study participation will be emphasized along with appropriate consent obtained as required per this protocol. Participation of not will not affect any relationship with this research team, the University of Minnesota or M Health.

Individual or group with a fear of negative consequences for not participating in the research (e.g. institutionalization, deportation, disclosure of stigmatizing behavior). Research staff will not be asking a direct questions of potential participants that could reveal such information. The voluntary nature of study participation will be emphasized along with appropriate consent obtained as required per this protocol. Participation of not will not affect any relationship with this research team, the University of Minnesota or M Health.

MEDICAL PROTOCOL (HRP-590)

PROTOCOL TITLE: Capillary Refill Time Measurement Utilizing Mobile Application (Cap App) in Children

VERSION DATE: 10/27/2022

Any other circumstance/dynamic that could increase vulnerability to coercion or exploitation that might influence consent to research or decision to continue in research. Research staff will not be asking a direct questions of potential participants that could reveal such information. The voluntary nature of study participation will be emphasized along with appropriate consent obtained as required per this protocol. Participation of not will not affect any relationship with this research team, the University of Minnesota or M Health.

Individual or group with a serious health condition for which there are no satisfactory standard treatments may be included unless exclusionary (see section 8.2). The study is non-interventional and will not impact care or treatment of the child, therefore felt that can be included in study enrollment. If there are questions, the research team will defer to the investigator for inclusion.

- 9.3 If research includes potential for direct benefit to participants, provide rationale for any exclusions indicated in the table above: NA/no direct benefit to participation

10.0 Local Number of Participants

- 10.1 Local Number of Participants to be Consented: A minimum of 240 participants are needed for data analysis and we anticipate needing to consent 300+ participants to meet that goal to account for errors in data collection, data upload, and/or participant withdrawal. We will attempt to match participants by age group and skin tone to control for expected variance of CRT measurement.

11.0 Local Recruitment Methods

- 11.1 Recruitment Process: Convenience sample of participants presenting at D2D: The Driven to Discover Research Facility at the Minnesota State Fair, August 25 - September 5, 2022.
- 11.2 Identification of Potential Participants: All participants interested in enrolling in our study presenting at the D2D: The Driven to Discover Research Facility at the Minnesota State Fair will be screened using the inclusion/exclusion criteria. We will then approach the parent/guardian for consent of children meeting the inclusion criteria.
- 11.3 Recruitment Materials: A conspicuous study sign will be made. The sign will have the following verbiage: "Cap App: a mobile health smartphone application to measure finger blood flow in children. You may be asked to participate in an optional research study to learn more about the utility of a new smartphone application that could one day improve the diagnosis of several medical conditions in children, including dehydration." This sign will be in the clearly visible in the D2D Research Facility at the Minnesota State Fair

MEDICAL PROTOCOL (HRP-590)

PROTOCOL TITLE: Capillary Refill Time Measurement Utilizing Mobile Application (Cap App) in Children
VERSION DATE: 10/27/2022

11.4 Payment: No payment will be provided but all participants will receive a complimentary University of Minnesota Backpack provided through D2D.

12.0 Withdrawal of Participants

12.1 Withdrawal Circumstances:

Participants are free to withdraw from participation in the study at any time upon request. An investigator may discontinue or withdraw a participant from the study for the following reasons:

- If any clinical adverse event (AE), or other medical condition or situation occurs such that continued participation in the study would not be in the best interest of the participant. This may include if there are any signs of discomfort (i.e. crying, tantrums, fits, screaming).
- If the participant meets an exclusion criterion (either newly developed or not previously recognized) that precludes further study participation

12.2 Withdrawal Procedures: If a participant/parent/guardian wishes to withdraw or we determine that the participant should withdraw, we will terminate data collection and discuss with the participant the reasons for withdrawal. All data collected up to that point will be used in analysis. This will be made known in the consent form.

12.3 Termination Procedures:

This study may be temporarily suspended or prematurely terminated if there is sufficient reasonable cause. Written notification, documenting the reason for study suspension or termination, will be provided by the suspending or terminating party to the funding agency. If the study is prematurely terminated or suspended, the PI will promptly inform the IRB and will provide the reason(s) for the termination or suspension. The study team will notify the participants of the study termination.

Circumstances that may warrant termination or suspension include, but are not limited to:

- Determination of unexpected, significant, or unacceptable risk to participants
- Demonstration of efficacy that would warrant stopping
- Insufficient compliance to protocol requirements
- Data that are not sufficiently complete and/or evaluable
- Determination that the primary endpoint has been met
- Determination of futility

The study may resume once concerns about safety, protocol compliance, and/or data quality procedures are addressed and satisfy the sponsor, IRB and/or FDA.

MEDICAL PROTOCOL (HRP-590)

PROTOCOL TITLE: Capillary Refill Time Measurement Utilizing Mobile Application (Cap App) in Children
VERSION DATE: 10/27/2022

Data collected for the study prior to the study termination will be handled in the following manner:

- If the study is terminated due to safety reasons, the data related to AEs will be evaluated.

If the study is terminated for any other reason, the regulatory and/or institutional document/data retention policies will apply.

13.0 Risks to Participants

13.1 Foreseeable Risks:

Although we cannot eliminate the loss of confidentiality or privacy, this study does involve the collection of private health information. All personal information will be assigned a random study identification number and stored on a secure database. The personal information of the participants will not be recorded in the study database.

The smartphone camera will only record participants' hand/fingertip so no sensitive information should be recorded by the smartphone camera. The smartphone has ability for video only so that audio is not applicable.

Nevertheless, participants will be made aware of the nature of the video recordings ahead of time and will have the option of having video recordings redone or deleted.

We will provide a brief explanation of the procedure to the participants old enough to understand (age >3 years) so that they can know what to expect with finger compression. The explanation will include language similar to: "Your fingertip will be squished tightly for 5 seconds, but then it will stop. You'll have this done four times on both your right and left finger, but we may ask you to have it happen again."

13.2 Reproduction Risks: NA

13.3 Risks to Others: NA

14.0 Potential Benefits to Participants

14.1 Potential Benefits: There are no direct benefits for participation in this study. This information will be used to help determine effectiveness of a mobile health application at measuring CRT in children.

15.0 Statistical Considerations

15.1 Data Analysis Plan: We plan to utilize a Biostatistical Design and Analysis Center biostatistician from the Clinical and Translational Science Institute in the statistical analysis of our data. We will compare the manual method of CRT (human annotation with a stopwatch and computer analysis) and Cap App measurement of CRT amongst each individual subject. We will then create a normal range of Cap App CRT based on

MEDICAL PROTOCOL (HRP-590)

PROTOCOL TITLE: Capillary Refill Time Measurement Utilizing Mobile Application (Cap App) in Children
VERSION DATE: 10/27/2022

age of the subject in one of five categories (1-3 months, 3-12 months, 1-5 years, 5-12 years, and 12-17 years), sex (male or female), and race (skin tone). We will include a description of the primary diagnosis, vital signs (heart rate, blood pressure, oxygen saturation), temperature (room, patient core, and skin), and second, third, and fourth measurements of CRT (used for intra-rater reliability). Missing data will be documented as noted and the record will be excluded from analysis as applicable. Minimal missing data is expected, so missing data will not be imputed.

15.2 Power Analysis: The goal of this study is to determine the precision of the capillary refill time measured via the smartphone application, so no formal power calculation was performed.

15.3 Statistical Analysis: We will recruit pediatrics patients aged 1 month to 17 years who are presenting to the D2D: The Driven to Discover Research Facility at the Minnesota State Fair. Descriptive statistics will be used to summarize the data collected. For the primary outcome, we will calculate mean CRT along with 95% confidence intervals, both overall and by age group, sex, and skin tone. We will attempt to enroll a minimum of 48 patients per age group for a total of 240 patients. Initial results showed an average standard deviation of 0.663 seconds across all patients at normal hand temperature. When the sample size is 48, a two-sided 95% confidence interval for a mean will extend ± 0.188 seconds. For a total sample size of 240, a two-sided 95% confidence interval for a mean will extend ± 0.084 seconds. Human annotation of a video recording using a stopwatch will be used to measure the manual CRT measurement and we will perform computer annotation of the video recording as a gold standard. For human and computer annotations we will calculate inter-rater reliability by repeating annotations with a different observer on 10% of a random group of CRT measurements. Inter-rater reliability will be evaluated using intraclass correlation coefficients (ICCs) and Bland–Altman plots.

15.4 Data Integrity: The research assistant will obtain study eConsent and fill the data collection forms which will be embedded into the Cap App and will be password protected. The data forms, video recordings for human and computer annotation, and Cap App CRT measurement will then be uploaded to a secure web-based data storage platform, Box. The research assistant will erase the data on the smartphones every shift and will store them in a secure location at all times. The *consent forms, assent forms, and case report forms* will be electronic (UMN REDCap eConsent). No paper copies will be utilized.

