3.0 Study Endpoints/Events/Outcomes

- 3.1 Primary Endpoint/Event/Outcome: Determining the accuracy and precision of a mobile health application (Cap App) to measure CRT in an otherwise healthy pediatric patient population.
- 3.2 Secondary Endpoint(s)/Event(s)/Outcome(s): To establish normal values of CRT via Cap App for healthy children of varying age ranges, determine if subject characteristics such as skin tone, skin temperature, sex, or age affect the CRT measured via the Cap App, and determine if the CRT measured via the Cap App correlates to the manual measurement of CRT in healthy children at varying age ranges.

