5.0 Procedures Involved

5.1 Study Design: The study design will be a cross-sectional study. The observation will be to collect the CRT from a population of healthy pediatric participants. Participants who meet the inclusion criteria will have their CRT measured using both the manual measurement (to include both human and computer annotation) and mobile health application (Cap App).

Study Procedures: **Cap App CRT measurement:** Children will be placed in a seated position, and their hand resting on a table top in a resting position. The research assistant will use a smartphone with the mobile health application (Cap App) to measure the CRT. The phone will be placed on a tabletop with the front facing camera face up. The subject's index fingertip will be placed onto the camera of the smartphone with minimal pressure. The finger will then be pressed firmly against the camera for a total of 5 seconds and then released from firm pressure while still contacting the camera with instructions from the Cap App. The research assistant then presses "stop" on the Cap App device. The Cap App will then measure the amount of time it takes for blood to refill the capillary bed as evidenced by the signal return to normal of light shining on the capillary bed. This measurement will be kept blinded to the researcher and be uploaded to a secure web-based cloud server, Box, for analysis. To establish the reproducibility of the index test (or the ability of the test to be accurately replicated), the CRT will be repeated at least twice on the index fingertip with at least 15 seconds between tests, and twice on the index finger of the opposite hand, all within 30 to 60 seconds of each other.

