Manual CRT measurement: Children will be placed in a seated position with their hand raised slightly above the level of the heart on a table. A tripod will be set up for the smartphone to video record the capillary refill test by facing the table from the top. The recording will begin, and audio will not be recorded. The research assistant will compress the index finger of the participant for 5 seconds with transparent plastic and then release the pressure, after which the plastic will be removed from the field of view of the camera. The camera recording will then be stopped once the research assistant has determined the color has returned to its original color. To establish the reproducibility of the index test (or the ability of the test to be accurately replicated), the CRT will be repeated at least twice on 1 fingertip with at least 15 seconds between tests, and twice on the index finger of the opposite hand, all within 30 to 60 seconds of each other. The video, without audio, will be stored in the University of Minnesota's secure online storage platform, Box. For analysis the research study team will complete the following:

- Human annotation from manual CRT measurement: The video will be annotated blindly by a separate research team member than the one who performs the CRT manual measurement. The CRT will be measured as the

MEDICAL PROTOCOL (HRP-590)

PROTOCOL TITLE: Capillary Refill Time Measurement Utilizing Mobile Application (Cap App) in Children

VERSION DATE: 10/27/2022

amount of time required for the index finger color to return to its pre-compressed color. The measurement will be annotated by a trained human from the video recording by measuring the CRT with a stopwatch, as is the current standard.

- Computer annotation from manual CRT measurement: The same video from the manual CRT measurement will be used for the computer annotation. A research team member will manually select a section of the finger for use in the analysis and then a computer will analyze the color using signal processing. This annotation will serve as the gold standard of what is possible for human visual CRT measurement.

Individually Identifiable Health Information: Electronic data collection forms will be used to collect all relevant variables to help interpret CRT measurements in the context of the healthy patient populations. In brief, the following is the information that will be collected:

1) For healthy participants:

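### Cap App and the computer reference are read from different presses, and the plan uses neither a suitable agreement measure nor the replicate readings to keep press-to-press variation apart from app disagreement

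*Combined protocol and SAP*

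**What the plan says.** Section 5.1 describes two separate compressions. For Cap App, "The finger will then be pressed firmly against the camera for a total of 5 seconds", with "their hand resting on a table top in a resting position". For the manual method, "The research assistant will compress the index finger of the participant for 5 seconds with transparent plastic", with the hand slightly above heart level and a tripod camera filming.

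Both manual readings come from that film. For the human reading, "The measurement will be annotated by a trained human from the video recording by measuring the CRT with a stopwatch". For the computer reading, "The same video from the manual CRT measurement will be used for the computer annotation", and "This annotation will serve as the gold standard of what is possible for human visual CRT measurement".

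Each method is repeated at least twice on one index finger and twice on the other, so about four presses per method per child.

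On analysis, section 15.1 says "We will compare the manual method of CRT (human annotation with a stopwatch and computer analysis) and Cap App measurement of CRT" within each subject. It gives no statistic, pairing rule or model, and it gives readings two to four a reliability role only. Section 3.2 sets out to "determine if the CRT measured via the Cap App correlates to the manual measurement of CRT in healthy children at varying age ranges". In section 15.3, ICCs and Bland-Altman plots are named only for repeat annotation by a second observer on 10% of measurements.

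**The concern.** The human and computer readings of one video share everything that happened in that press. A Cap App reading and a computer reading share only the child. Their difference therefore carries the press-to-press variation of both methods on top of any app error, while a human-computer difference carries none.

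The one app-versus-manual statistic the plan names, correlation, is attenuated by that variation. It is also blind to a shift in level, and section 2.1 reports that in the adult pilot the app read longer overall than the manual method.

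Accuracy and precision are the stated purpose (section 1.1) and the primary outcome (section 3.1). A good app could show wide limits and a modest correlation for reasons that are not its own, and an app that reads long could keep a high correlation. The replicates that could sort this out are collected but not assigned to the comparison.

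**Working it through.** **Inputs.** SD 0.663 s, n = 48 and n = 240 (section 15.3); about four presses per method (section 5.1). The split of variance within and between children is not in the documents, so it is assumed below.

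**The plan's own figures.** Half-width = 1.96 × SD/√n.
- n = 48: 1.96 × 0.663/√48 = 0.188 s.
- n = 240: 1.96 × 0.663/√240 = 0.084 s.

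Both reproduce. They concern mean CRT, not agreement, and are not in dispute.

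**Variance components.** Write a reading as child value + press deviation + reading error.
- App minus computer: variance = 2 × press variance + app error variance + computer error variance.
- Human minus computer, one video: variance = human error variance + computer error variance. The press term cancels.
- In both cases random press deviations average to zero, so the mean difference is not biased.

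**A perfect app and perfect readers.** Let ICC be the between-child share of 0.663², equal for both methods (assumption). Then:
- within-child SD = 0.663 × √(1 − ICC)
- single-press limits = ±1.96 × √2 × within-child SD
- maximum single-press correlation = ICC
- for means of four, the limits halve and the maximum correlation = ICC/(ICC + (1 − ICC)/4)

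| Between-child share | Within-child SD (s) | Limits, single press (s) | Max. correlation, single press | Limits, mean of four (s) | Max. correlation, mean of four |
|---|---|---|---|---|---|
| 0.3 | 0.555 | ±1.54 | 0.30 | ±0.77 | 0.63 |
| 0.5 | 0.469 | ±1.30 | 0.50 | ±0.65 | 0.80 |
| 0.7 | 0.363 | ±1.01 | 0.70 | ±0.50 | 0.90 |
| 0.9 | 0.210 | ±0.58 | 0.90 | ±0.29 | 0.97 |

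Human against computer on the shared video would show limits of 0 and a correlation of 1 in every row.

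**With equal reading error.** Assume an error SD of 0.1 s for all three readings.
- Human-computer limits: 1.96 × √(2 × 0.1²) = ±0.28 s, whatever the press share.
- App-computer limits: 1.96 × √(2f × 0.663² + 2 × 0.1²), where f is the press share. This gives ±0.64, ±1.04 and ±1.33 s for f = 0.1, 0.3 and 0.5.

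The app is exactly as good a reader as the other two in this example.

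**Do the replicates solve it?** In a simulation of 240 children with four presses per method (1000 runs, f = 0.1, 0.3, 0.5), removing within-child variance gave an app-computer correlation of about 1.00 and an excess between-child difference variance of about 0. Both are right for the simulated app. Mean bias was about 0 throughout. Averaging four presses without that correction helps only in part, as the table shows.

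**The case against.** The strongest reply is that section 15.1 only says the methods will be compared. It does not commit to single-press limits of agreement, and any paired comparison of means would reveal an app that reads long. That stands, and it limits the point to spread and correlation. It does not remove it: section 3.2 does name correlation, and section 15.1 does send the replicates elsewhere.

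Several stronger readings are tempting, and the documents do not support them.
- A reader might infer that the accuracy question as a whole will be answered wrongly. Random press variation leaves the mean app-minus-computer difference unbiased.
- A reader might infer that the plan will rank the app below the stopwatch. No such ranking is planned; section 1.1 treats both manual methods as comparators.
- A reader might take the pilot to report a constant offset. Section 2.1 says the app reads longer overall, varies more in the cold, and tends to overestimate in darker skin, which suggests a shift that depends on the child.
- A reader might say nothing will show the press noise. Intra-rater reliability would reveal some of it; what is missing is its use in the comparison.
- A reader might argue that healthy children have a narrow CRT range, which lowers the correlation further. No range is given, and section 2.0 cites marked age and sex variation.

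The magnitude is also fairly contested. The variance split is assumed, section 15.3 does not say which method the 0.663 s belongs to, and means of four roughly halve the limits.

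**Conclusion.** The point holds in this form: if sections 15.1 and 3.2 are followed as written, press-to-press variation widens the app-computer spread and lowers the correlation, and the named measure cannot detect a shift in level. The mean difference is not biased by it.

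The size is a range under assumption. For a perfect app with 30-70% of the variance between children, limits are about ±1.5 to ±1.0 s and correlation at most 0.3-0.7 on single presses, or about ±0.8 to ±0.5 s and 0.63-0.90 on means of four. If only 10% of the variance is press-to-press, the single-press figures are ±0.58 s and 0.90. These rest on 0.663 s being the total SD of one reading and applying equally to both methods.

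This is more than missing detail, because the stated measure and the stated use of replicates give a poorer answer than the same data allow. The plan should be changed; the study's measurements and its precision figures for mean CRT are unaffected.

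**What to change.** - **Section 15.1.** Use all replicate readings in the Cap App versus computer comparison, through a mixed model with method, hand, child, child-by-method and method-specific residual terms, or an equivalent repeated-measures Bland-Altman analysis. Report the mean bias with 95% CI, the child-by-method SD and each method's within-child SD.
- **Benchmark.** Set app-computer agreement against computer readings on different presses of the same child. If human-computer agreement is shown alongside, state that it comes from one shared press.
- **Section 3.2.** Make bias and limits of agreement by age group the measures, with correlation as a supplement only.
- **Stated limit.** Hand position and compression technique differ between methods (section 5.1), and no model can separate their effect from the app's. Say that the bias and child-by-method SD describe the whole measurement procedure, not app error alone.

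The cost is revised analysis wording and a little more analysis work. The replicates are already in section 5.1, so no new measurement is needed.
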